#### Electronic Serious Adverse Event (eSAE) Reporting Process

- Site personnel record all SAE data in the eCRF database and from there transmit the SAE information to Gilead Drug Safety and Public Health (DSPH) within 24 hours of the investigator's knowledge of the event. Detailed instructions can be found in the eCRF completion guidelines.
- If for any reason it is not possible to record the SAE information electronically, i.e., the eCRF database is not functioning, record the SAE on the paper serious adverse event reporting form and submit within 24 hours to:

Gilead Sciences DSPH:	Fax:	PPD [REDACTED]
	E-mail:	PPD [REDACTED]
Gilead Sciences Study Director / Medical Monitor:	Name:	PPD [REDACTED]
	Telephone:	PPD [REDACTED]
	Mobile:	PPD [REDACTED]
	Fax:	PPD [REDACTED]
	Email:	PPD [REDACTED]

- As soon as it is possible to do so, any SAE reported via paper must be transcribed into the eCRF Database according to instructions in the eCRF completion guidelines.
- If an SAE has been reported via a paper form because the eCRF database has been locked, no further action is necessary.
- For fatal or life-threatening events, copies of hospital case reports, autopsy reports, and other documents are also to be submitted by e-mail or fax when requested and applicable. Transmission of such documents should occur without personal subject identification, maintaining the traceability of a document to the subject identifiers.
- Gilead Sciences may request additional information from the investigator to ensure the timely completion of accurate safety reports.
- Any medications necessary for treatment of the SAE must be recorded onto the event description section of the SAE form.

The investigator must take all therapeutic measures necessary for resolution of the SAE. Follow-up of SAEs will continue through the last day on the Registry and/or until a conclusive outcome (eg, resolved, resolved with sequelae, lost to follow-up, fatal) is achieved.

### **7.3.2. Investigator and Sponsor Reporting Requirements for SAEs**

Any SAE deemed by the investigator to be related to a protocol-required procedure should be collected and reported throughout the Registry study and reported to Gilead Sciences DSPH using the SAE report form.

An SAE may qualify for reporting to regulatory authorities. All Investigators will receive a safety letter notifying them of relevant SUSAR reports. The Investigator should notify the IRB/IEC as soon as is practical, of serious events in writing where this is required by local regulatory authorities, and in accordance with the local institutional policy.

In accordance with the EU Clinical Trials Directive (2001/20/EC), Gilead will notify worldwide regulatory authorities and the relevant Ethics Committees in concerned Member States of applicable SUSARs.

### **7.4. Clinical Laboratory Abnormalities and Other Abnormal Assessments as Adverse Events or Serious Adverse Events**

Lab abnormalities are usually not recorded as AEs or SAEs. Laboratory abnormalities will only be recorded as an AE/SAE if they are related to a protocol required procedure.

### **7.5. Procedures to be followed in the Event of Pregnancy**

Procedures to be followed in the event of pregnancy occurring on the treatment protocol are detailed in the Gilead-sponsored treatment protocol. No additional pregnancy reporting requirements are included in this Registry protocol.

## 8. STATISTICAL CONSIDERATIONS

### 8.1. Analysis Objectives and Endpoints

Treatment regimen is defined in the Gilead-sponsored treatment protocol.

#### 8.1.1. Analysis Objectives

The primary objectives of this study are:

- To assess the durability of SVR;
- To assess clinical progression or regression of liver disease, including the incidence of hepatocellular carcinoma (HCC) following SVR

The secondary objective of this study is:

- For subjects who received their SOF-based regimen in a Gilead parent protocol, to determine whether subsequent detection of HCV RNA in subjects who relapse following SVR represents the re-emergence of pre-existing virus, the development of resistance mutations, or re-infection

The exploratory objective of this study is:

- CCI [REDACTED]

#### 8.1.2. Primary Endpoints

The primary endpoints are:

- The proportion of subjects maintaining SVR at Week 240;
- The proportion of subjects who develop liver disease progression or regression, as assessed by clinical and laboratory parameters;
- The proportion of subjects who develop HCC through Week 240

#### 8.1.3. Secondary Endpoints

The secondary endpoints will be assessed in subjects who received their SOF-based regimen in a Gilead parent protocol, as follows:

- The proportion of subjects with detectable HCV RNA due to re-emergence of pre-existing virus through Week 240;
- The proportion of subjects with detectable HCV resistance mutations through Week 240
- The proportion of subjects with detectable HCV RNA due to re-infection through Week 240

#### **8.1.4. Other Endpoints of Interest**

CCI

█

█

#### **8.2. Analysis Conventions**

All individual subject data will be listed as measured. All statistical summaries and analyses will be performed using SAS® software (SAS Institute, Cary, North Carolina, USA).

##### **8.2.1. Analysis Sets**

###### **8.2.1.1. Safety Analysis Set**

The analysis set includes all enrolled subjects. Both the safety and efficacy analyses will be based on the safety analysis set.

#### **8.3. Data Handling Conventions**

Missing data can have an impact upon the interpretation of the trial data. In general, values for missing data will not be imputed.

All available data for subjects who do not complete the study will be included in data listings.

HCV RNA values below the LLOQ for the assay will be set to the lower limit minus 1 for calculation of summary statistics for the actual HCV RNA values and the change from baseline values by study visit. The reported values will be provided in the HCV RNA listing.

For selected analyses of early time point data, HCV RNA data (IU/mL) may be transformed to the logarithmic (base 10) scale ( $\log_{10}$  IU/mL).

#### **8.4. Interim Analyses**

Interim analyses may be performed on an ad hoc basis.

#### **8.5. Demographic Data and Baseline Characteristics**

Demographic and baseline measurements will be summarized using standard descriptive methods.

Demographic summaries will include sex, self-identified race/ethnicity, and age.

Baseline characteristics data will include a summary of HCV RNA levels, liver function tests, platelets, coagulation test,  $\alpha$ -fetoprotein, and HCV genotype and IL28B genotype, if known.

## **8.6. Efficacy Analysis**

All continuous endpoints will be summarized using an 8-number descriptive summary (n, mean, standard deviation, median, Q1, Q3, minimum and maximum). All categorical endpoints will be summarized by the number and percent of subjects meeting the endpoint. Ninety-five percent confidence intervals will also be reported.

### **8.6.1. Primary Analysis**

The proportion of subjects who maintain an SVR through Week 240 will be estimated using a Kaplan-Meier model, allowing for censored observations due to early discontinuation from the Registry.

The proportion of subjects who develop clinical progression or regression of liver disease through Week 240 will be estimated using a Kaplan-Meier model, allowing for censored observations due to early discontinuation from the Registry.

The proportion of subjects who develop HCC through Week 240 will be estimated using a Kaplan-Meier model, allowing for censored observations due to early discontinuation from the Registry.

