6.1. Primary Endpoints

6.1.1. Definition of the Primary Endpoints

The primary endpoints are:

- The proportion of participants maintaining SVR at Week 240;
- The proportion of participants who develop liver disease progression or regression, as assessed by clinical and laboratory parameters;
- The proportion of participants who develop HCC through Week 240.

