6.1.3.2. Proportion of Participants Who Develop Liver Disease Progression or Regression

6.1.3.2.1. Liver Disease Assessment Including Hepatocellular Carcinoma

Events related to liver disease progression include:

- Hepatic encephalopathy
- Hepatocellular carcinoma (HCC)
- Hepatorenal syndrome
- Hepatopulmonary syndrome
- Portopulmonary hypertension
- Hepatic hydrothorax
- Bleeding varices
- Spontaneous bacterial peritonitis
- Liver Transplant
- Ascites
- Liver-related death

Hepatic decompensation events include:

- Hepatorenal syndrome

- Hepatopulmonary syndrome
- Portopulmonary hypertension
- Hepatic hydrothorax
- Hepatic encephalopathy
- Bleeding varices
- Spontaneous bacterial peritonitis
- Ascites
- Liver-related death

Except for ascites (using data collected from liver imaging)/liver transplant/death, other events will be all collected from liver disease assessment page in eCRF. Minimal or trace ascites will not be treated as a liver event. Liver-related death will be identified by Clinical Research based on the immediate cause of death.

Participants with events related to liver disease progression that were identified prior to registry start date will be excluded from the analysis but will be listed.

Participants with De Novo HCC since registry start are defined as participants who were not identified with HCC prior to registry start and only had HCC since registry start.

Summary of participants with liver events will be provided, including the percentage of participants with events among FAS, the percentage of participants for each type of events among all the participants with events, and the percentage of participants with any event prior to registry start among FAS.

Person-time pertaining to KM analysis of time to events in this section will be calculated as: first event date (for participants who experienced events) or last day of registry (for participants who did not experience events) – registry start date + 1.

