For time to first liver event since registry start, KM estimate of the proportion of participants with events related to liver disease progression, the cumulative number of participants who experienced events, were at risk, and had been censored will be summarized by treatment group and time point (Week 0, 24, 48,..., 216, and 240), where Week 0 to 216 are the exact weeks elapsed since registry start date (i.e., 0, 168, 336,..., and 1512 days), and Week 240 includes 1680 days elapsed since registry start date plus additional 30 days (i.e. 1710 days). Participants with liver events prior to registry start will be excluded from this analysis.

Same summary table as above will be provided separately for participants with De Novo HCC, with hepatic decompensation events, with liver transplant, and with all-cause death.

Same summary tables will be provided for above endpoints by baseline CTP class (CTP A, B, C, Unknown and total). Time to the first liver event and time to De Novo HCC since registry start will be summarized descriptively (n, mean, SD, median, Q1, Q3, minimum, and maximum) in a table for those participants with events occurring only during the registry study.

The KM plots will also be presented in a figure.

A by-participant, by visit listing of participants who developed above events will be provided by participant ID number in ascending order (events prior to registry start will be flagged). A separate listing will be provided for participants with De Novo HCC since registry start. Participants who experienced an HCC event more than 30 days after 240 weeks elapsed since registry start date (i.e. > 1710 days)/participants with HCC prior to registry start date will be listed separately.

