6.5. Changes from Protocol-Specified Endpoint Analyses

No change from protocol-specified endpoint analysis is planned.

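### Protocol 8.6.1 promises a Kaplan-Meier proportion that includes regression of liver disease, but neither document defines a regression event, the SAP runs no such analysis, and SAP 6.5 declares no change

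*Protocol*

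**What the plan says.** Regression is part of a primary objective in both documents and part of a primary endpoint. Protocol 8.1.2 words the endpoint as "The proportion of subjects who develop liver disease progression or regression, as assessed by clinical and laboratory parameters". Protocol 8.6.1 sets the method: "The proportion of subjects who develop clinical progression or regression of liver disease through Week 240 will be estimated using a Kaplan-Meier model", with censoring at early discontinuation. Protocol 8.6 adds 95% confidence intervals.

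SAP 6.1.1 carries the endpoint over: "The proportion of participants who develop liver disease progression or regression, as assessed by clinical and laboratory parameters". The heading of SAP 6.1.3.2 is "Proportion of Participants Who Develop Liver Disease Progression or Regression".

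The event list below that heading opens with "Events related to liver disease progression include", and the time-to-event analysis is a "KM estimate of the proportion of participants with events related to liver disease progression". The same table is then repeated "separately for participants with De Novo HCC, with hepatic decompensation events, with liver transplant, and with all-cause death".

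SAP 6.5 closes the endpoint section with "No change from protocol-specified endpoint analysis is planned".

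**The concern.** Whether liver disease improves after cure is one of the registry's main questions, and the protocol gives that question a primary analysis. A team that follows the SAP exactly will produce no Kaplan-Meier proportion for regression, while the SAP tells the reader that nothing has changed.

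Two things are at stake. First, with no measure named in advance, a regression rate quoted in the report could come from any of several markers and visits, chosen after the tables are seen. Second, tables by visit do not answer the question the protocol asks. The same count of improved participants at two visits may be the same people or different people, so the tables do not give the proportion who had improved at any time through Week 240.

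**Working it through.** The documents give no sample size, power or event count for this endpoint, so there is no planned figure to reproduce. The check is a comparison of text, with one count.

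**1. Is a regression event defined?** Protocol 8.1.2 and 8.6.1 give no parameter, threshold or date of onset. In the SAP, regression is named only in the primary objective (1.1), the endpoint list (6.1.1) and the heading of 6.1.3.2. SAP 6.1.3.2.1 lists 11 progression events and 9 decompensation events, and no event that represents improvement. No text is blacked out in SAP 6.1.3.2, so redaction does not explain the gap.

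**2. Which outcomes have a time-to-event summary in SAP 6.1.3.2.1?** Any progression event, de novo HCC, hepatic decompensation, liver transplant and all-cause death. None of these five is regression.

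**3. Where could improvement be seen?**

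| Shift table | SAP section | Categories | Post-baseline visits |
|---|---|---|---|
| FibroTest stage | 6.1.3.2.2 | three stages, no numeric limits given | up to 10 |
| ELF class | 6.1.3.2.2 | 9.8 and 11.3 | up to 10 |
| FIB-4 | 6.1.3.2.2 | change of at least 25% either way | up to 10 |
| CTP class | 6.1.3.2.3 | A, B, C | up to 10 |
| MELD | 6.1.3.2.3 | below 15, or 15 and above | up to 10 |
| Varices grade | 6.4.2 | none, small, large, unknown | 1 (Week 240) |
| Elastography | 6.4.3 | 9.5 and 12.5 kPa | 5 |

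The SAP also gives change-from-baseline summaries for laboratory tests, MELD and elastography. None of this content is labelled regression, has an onset date or is accumulated through Week 240. Varices and elastography are placed under other measurements, not under the primary endpoint.

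**4. How many candidate results does that leave?** For the Total column alone: 5 markers × 10 visits + 5 elastography visits + 1 varices comparison = 50 + 5 + 1 = 56 marker-by-visit comparisons. This is an upper limit. It assumes that the CTP and elastography shift tables are produced at every scheduled visit, which the SAP does not say outright.

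**5. Can the protocol sentence be run as written?** No. It joins progression and regression in one proportion. Taken literally, a participant who worsened and one who improved would count as the same event. The two have to be separated, and Protocol 8.10 leaves further methods to the SAP.

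**6. Is SAP 6.5 accurate?** Protocol 8.6.1 includes regression in a Kaplan-Meier estimate and the SAP does not. That is a change, and 6.5 declares none.

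**7. Would the existing at-risk set serve?** SAP 6.1.3.2.1 leaves participants with liver events before registry start out of the Kaplan-Meier analysis of progression. Ascites and encephalopathy are on that event list and are also components of the CTP score. The exclusion could therefore remove many of those in class B or C at Day 1, who are the participants with room to improve by CTP class. The documents do not give the number.

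**The case against.** The strongest reply is that the SAP does report improvement. Five of the seven shift tables sit under the 6.1.3.2 heading, the endpoint is to be judged on clinical and laboratory parameters, and these are such parameters. FIB-4 has an explicit reduction class, and the proportion in each CTP class is given by visit. Protocol 8.6.2 itself plans descriptive summaries of laboratory results and clinical signs related to progression or regression, and the SAP tables largely carry that out. This stands. A reader might infer that the SAP says nothing about improvement, or that half of a primary endpoint goes wholly unreported. The documents do not support either. What is missing is a designated regression measure and its cumulative proportion. Protocol 8.6.2 covers secondary analyses and does not cancel the commitment in 8.6.1.

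A second reply is that the fault starts in the protocol. This also stands. A reader might infer that the SAP dropped a defined analysis, but the protocol never defined one, and its pooled sentence could not sensibly be run.

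A third is that the cut-offs are fixed. That is right for ELF, FIB-4, CTP, MELD and elastography, so it would be wrong to say that thresholds are open to choice after the data are seen. Among the laboratory and elastography measures, only the FibroTest stages lack numeric limits. The choice of marker and visit remains open.

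Finally, no hypothesis is tested (SAP 3.5 and 6.1.2). A descriptive estimate still needs a definition, and selective reporting does not depend on a p-value.

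**Conclusion.** The point holds as a mismatch between the documents and a missing definition. The protocol's Kaplan-Meier proportion for regression has no event definition in either document and no analysis in the SAP (0 of 5 time-to-event summaries), and the no-change statement in SAP 6.5 is incorrect. Regression is described by seven pre-specified shift tables and by change-from-baseline summaries, mostly with fixed cut-offs, but no planned regression proportion comes out of them. Up to 56 marker-by-visit comparisons in the Total column could be read as one, on the assumption in step 4.

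The progression, HCC, decompensation, transplant and death estimates are not affected. The point does not show that any result would be biased or selectively reported, only that the plan leaves room for it. It should be corrected because the correction is specific and cheap.

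**What to change.** In SAP 6.1.3.2, name one regression measure from data already collected. One example is a fall of at least one CTP class among those in class B or C at Day 1; other measures could serve. For the chosen measure:

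- State the at-risk set, and say that the exclusion of participants with liver events before registry start does not apply to this analysis.
- State the onset date (for example, the first visit at which the criterion is met, recognising that the change occurred at some point since the previous visit) and any confirmation rule. If confirmation is required, say how a first improvement at Week 240 is handled, since no later scheduled visit can confirm it.
- Report the cumulative proportion through Week 240 separately from progression, with 95% confidence intervals and with death and transplant as competing events.
- Keep the shift tables as support.

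The SAP was signed on 10 May 2022, and SAP 1 sends later changes to the study report. If the measure is set after data review, label it post hoc there.

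At a minimum, correct SAP 6.5 to state that regression will be described only by shift tables, that this is a change from Protocol 8.6.1, and that no regression proportion will be claimed.

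The full fix costs some SAP text and one further time-to-event table, with no new data collection. The minimum costs a few lines. The downsides of the full fix are late specification and, for a CTP-based measure, possibly small numbers in class B or C, so the interval may be wide. A measure based on elastography would be limited to sites with the equipment.

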3.8. Visit Windows

3.8.1. Definition of Visits

Baseline Value will be the first non-missing value taken on or within 30 days of the registry start date (i.e., Day 1 Visit of the registry collected from the demographic eCRF). For questionnaire data, if no data are available within 30 days after the registry start date, the baseline value will be the last non-missing value prior to the registry start date.

Study days are calculated relative to registry start date as follows:

- For measurements that are collected before the registry start date: Visit date – registry start date.
- For measurement or events that are collected on or after the registry start date: Visit date – registry start date +1.

Last Day of the registry is the last recorded non-missing visit or collected data/assessment date in the database. When determining the last day of the registry, partial date will be imputed as 01 if only day is missing and 01 January if day and month are missing.

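### The primary HCC proportion is estimated by Kaplan-Meier with death and transplant censored, so 1-KM overstates the cumulative incidence whenever such an event precedes a later HCC

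*Protocol*

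**What the plan says.** Protocol 8.1.2 lists among the primary endpoints "The proportion of subjects who develop HCC through Week 240"; SAP 6.1.1 repeats it. Protocol 8.6.1 says that "The proportion of subjects who develop HCC through Week 240 will be estimated using a Kaplan-Meier model", with early discontinuation censored. Liver transplant ends registry participation (Protocol 3.2).

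SAP 6.1.3.2.1 runs person-time to the "first event date (for participants who experienced events) or last day of registry (for participants who did not experience events". SAP 3.8.1 adds: "Last Day of the registry is the last recorded non-missing visit or collected data/assessment date in the database". No separate rule covers death or transplant in the HCC analysis. For HCC itself the SAP says: "Same summary table as above will be provided separately for participants with De Novo HCC". All-cause death and transplant get their own Kaplan-Meier tables, but in the HCC table they are neither events nor competing events. Neither document names a competing-risk method, and SAP 6.5 plans no change from the protocol.

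On the risk set, SAP 6.1.3.2.1 gives two readings. Participants with progression events "identified prior to registry start date will be excluded from the analysis but will be listed", and the paragraph just before the HCC table repeats: "Participants with liver events prior to registry start will be excluded from this analysis". The definition of the endpoint is narrower: "Participants with De Novo HCC since registry start are defined as participants who were not identified with HCC prior to registry start".

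**The concern.** A participant who has died without HCC cannot develop it later. Kaplan-Meier with that death censored redistributes the person's weight to those still under observation, so 1-KM estimates the HCC proportion in a setting where death does not occur. The endpoint is worded as the proportion who develop HCC, and readers will take the result as that.

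For death, this is a mismatch between estimator and stated proportion. For transplant it depends on the estimand, which the documents do not state: HCC before transplant, or HCC regardless of transplant.

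The size of the bias rises with mortality, so columns by baseline CTP class could be overstated unequally. By how much depends on the unresolved risk set: if any earlier liver event leads to exclusion, many participants with previous decompensation drop out of the table.

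**Working it through.** **Direction.** At each HCC time, with d1 HCC events among n at risk:

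- 1-KM = sum of S_HCC(t-) × d1/n, where S_HCC falls only at HCC events.
- Aalen-Johansen = sum of S_all(t-) × d1/n, where S_all also falls at HCC-free death and transplant.

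S_all never exceeds S_HCC, so 1-KM is never below Aalen-Johansen on the same data. They are equal only if no competing event precedes an HCC. Example with 10 participants and no dropout: HCC at times 1 to 4 and deaths at 5 to 10 give 0.400 for both. Move one death before the last HCC and 1-KM = 1 − (9/10)(8/9)(7/8)(5/6) = 0.417, while the proportion with HCC is still 0.400.

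In 2,000 simulated data sets (500 participants each, assumed 8% per year dropout), 1-KM was strictly higher in every one.

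**Size.** The plan states no expected HCC proportion or sample size, so there is no figure to reproduce. Inputs, used as illustrative constant hazards:

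- Horizon T = 1710/365.25 = 4.682 years (SAP 6.1.3.2.1).
- HCC h = 0.01, 0.02, 0.04 per year (Protocol 1.1: 1 to 4% per year).
- Death o, from Protocol 1.2: compensated −ln(0.91)/5 = 0.0189; decompensated −ln(0.50)/5 = 0.1386; also half the latter, 0.0693.
- Transplant x: the documents give no rate; 0, 0.01 and 0.03 per year assumed.

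1-KM = 1 − exp(−hT) = 4.57 / 8.94 / 17.08%.

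Cumulative incidence = h/(h+o+x) × [1 − exp(−(h+o+x)T)]:

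| Competing events | Cumulative incidence at h = 1 / 2 / 4% | 1-KM excess, relative | Excess, points |
|---|---|---|---|
| Compensated death only | 4.38 / 8.56 / 16.37% | about 4% | 0.2 to 0.7 |
| Half decompensated death only | 3.91 / 7.65 / 14.66% | about 17% | 0.7 to 2.4 |
| Decompensated death only | 3.37 / 6.61 / 12.69% | about 35% | 1.2 to 4.4 |
| Compensated death + transplant 1% | 4.28 / 8.37 / 16.01% | about 7% | 0.3 to 1.1 |
| Compensated death + transplant 3% | 4.09 / 8.00 / 15.32% | about 12% | 0.5 to 1.8 |
| Decompensated death + transplant 1% | 3.30 / 6.47 / 12.44% | 37 to 38% | 1.3 to 4.6 |
| Decompensated death + transplant 3% | 3.17 / 6.22 / 11.95% | 43 to 44% | 1.4 to 5.1 |

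**Against sampling error.** The 95% half-width is 1.96 × sqrt(p(1−p)/N) at p = 4.57 / 8.94 / 17.08%, with N per CTP column assumed. N = 50 gives 5.8 / 7.9 / 10.4 points; N = 200 gives 2.9 / 4.0 / 5.2. These exceed every death-only gap. With decompensated mortality, transplant at 3% and HCC at 4% per year, gap and half-width are about equal (5.1 against 5.2 at N = 200). The formula ignores censoring, so real intervals are wider.

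**Whether the planned crude percentage fills the gap.** With assumed dropout c = 0.05 per year and h = 0.02, the crude proportion is h/(h+o+c) × [1 − exp(−(h+o+c)T)]:

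| Mortality | Crude | Cumulative incidence | 1-KM |
|---|---|---|---|
| Compensated | 7.7% | 8.6% | 8.9% |
| Decompensated | 6.0% | 6.6% | 8.9% |

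Crude errs low because it ignores dropout; 1-KM errs high. No planned figure handles both.

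**The case against.** The strongest point against is that the large figures may describe people who are not in the table. If any prior liver event leads to exclusion, most participants with earlier decompensation are gone and the compensated row is the relevant one: under one point for death alone. Even that row may be high. The 91% survival is a pre-SVR figure and includes deaths after HCC, and Protocol 1.2 itself links SVR to lower mortality. The transplant rows rest on an assumed rate, and transplants performed after HCC do not compete with it. This stands as a limit on size; it does not change the direction.

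The comparison is also with the cumulative incidence estimated on the same participants. By sampling error, 1-KM fell below the true cumulative incidence in 3% to 46% of data sets across the simulated scenarios.

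The plan offers partial mitigation: crude percentages (Protocol 8.6.2, SAP 6.1.3.2.1), numbers at risk and censored, separate death and transplant tables, and by-participant listings. The first-liver-event composite already counts transplant and liver-related death as events. A reader could gauge the gap from these but could not read off the right proportion.

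Finally, SAP 7 says deaths and their dates were recorded when available, so the remedy is incomplete. If half of the deaths were unrecorded and so censored (HCC 2% per year, decompensated mortality), Aalen-Johansen would give 7.65%, against a true 6.61% and 1-KM of 8.94%: better than 1-KM, but not fully corrected.

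**Conclusion.** The concern holds. A primary proportion is estimated by a method that can err in only one direction relative to the same-data cumulative incidence, and confidence intervals do not show that bias. It is small at compensated background mortality and material at decompensated mortality, if such participants are in the risk set. These sizes rest on constant hazards and the protocol's pre-SVR background rates.

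No test is affected, since the study is descriptive, and 1-KM still reflects the cause-specific HCC rate. At an assumed 50 to 200 participants per CTP column, sampling error exceeds the death-only bias, but the bias does not shrink as numbers grow. The change should be made: the direction is known, the endpoint is primary and the remedy is cheap.

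**What to change.** In SAP 6.1.3.2.1:

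- Settle the risk set first: say whether the De Novo HCC table excludes participants with any prior liver event or only those with prior HCC.
- Report the Aalen-Johansen cumulative incidence of De Novo HCC overall, by regimen and by baseline CTP class. Treat HCC-free death and liver transplant as competing events, and state the estimand as HCC before transplant, which matches transplant ending registry participation.
- Keep the protocol-specified 1-KM beside it, labelled as a cause-specific supplement.
- Record the departure from Protocol 8.6.1 in SAP 6.5 or the CSR.

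Optionally, and with less to gain, use the same approach for the transplant table (death competing), decompensation and the first-event composite.

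The cost is SAP wording, a standard cumulative-incidence routine and a second set of estimates to explain. Death and transplant already feed planned time-to-event tables. The HCC table needs the fact and date of death, not its cause; the report should note that unrecorded deaths remain censored.
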